4.1. Protocol Deviations

Important protocol deviations (including deviations related to study inclusion/exclusion criteria, conduct of the trial, patient management or patient assessment) will be summarised and listed.

Important deviations which result in exclusion from the analysis population will also be summarised and listed. (Please refer to [Appendix 1](#): Protocol Deviation Management and Definitions for Evaluable Population).

Protocol deviations will be tracked by the study team throughout the conduct of the study in accordance with the Protocol Deviation Management Plan Version 1.0 (Dated: 18/JUN/2018).

- Data will be reviewed prior to unblinding and freezing the database to ensure all important deviations and deviations which may lead to exclusion from the analysis are captured and categorised on the protocol deviations dataset.
- This dataset will be the basis for the summaries and listings of protocol deviations.

A separate summary and listing of all inclusion/exclusion criteria deviations will also be provided. This summary will be based on data as recorded on the inclusion/exclusion page of the eCRF.

5. CONSIDERATIONS FOR DATA ANALYSES AND DATA HANDLING CONVENTIONS

5.1. Study Treatment & Sub-group Display Descriptors

Treatment Group Descriptions			
RandAll NG		Data Displays for Reporting	
Code	Description	Description	Order in TLF
A	Placebo	Placebo	1
B	GSK2798745	GSK2798745	2

Treatment comparisons will be displayed as follows using the descriptors as specified:

1. GSK2798745 vs. Placebo

Parameter	Study Assessments Considered as Baseline					Baseline Used in Data Display
	Screening (Days -28 to -2)	Day -1	Day 1 Pre-dose	Day 1 1h	Day 1 2h ¹	
Pharmacodynamic						
BAL Total Protein					X	Day 1 2h
BAL Neutrophil Count (Total and Differential)					X	Day 1 2h
Safety						
12-lead ECG ²	X	X	X			Day 1 Pre-dose
Vital signs (blood pressure, heart rate) ³	X	X	X	X		Day 1 Pre-dose
Temperature	X	X	X	X	X	Day 1 Pre-dose
Spirometry (FEV1, FVC) ⁴		X	X			Day 1 Pre-dose
Laboratory assessments ⁵		X				Day -1
Exploratory Biomarkers						
BAL Biomarkers					X	Day 1 2h

NOTES:

1. Immediately before BAL sampling/LPS challenge
2. Triplicate at Screening, day-1 and day 1 pre-dose. Single measurements at time points after dosing.
3. Blood pressure and heart rate in triplicate.
4. Forced expiratory volume in 1 second (FEV1) and forced vital capacity (FVC). Triplicate measurements at each time point, the highest of which should be recorded in the case report form.
5. Haematology, clinical chemistry (including liver chemistry), cardiac troponins, urianalysis and coagulation profile.

5.2. Baseline Definitions

If the “baseline used in data display” is missing for a parameter, then the study assessment considered as a baseline closest in time to this will replace this as the baseline used in displays. If all study assessments considered as baseline are missing then no derivation will be performed and baseline will be set to missing.

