## 2.2. Treatment period

	Day -1 	Day 1 									Day 2 			Day 4	
		Pre-dose	0 h	1 h	2 h	3 h	6 h	8 h	12 h	14 h	25.5 h	26 h	30 h		
Inpatient stay 		←-----→													
Telephone call 															X
Drug, alcohol and cotinine screen	X														
Laboratory assessments 	X												X		
12-lead ECG 	X	X											X		
Blood pressure and heart rate 	X	X		X			X		X	X			X		
Temperature 	X	X		X	X		X	X	X	X			X		
Spirometry 	X	X					X					X	X		
C-SSRS													X		
Randomisation		X													
Study treatment			X						X						
Pulse oximetry 					X							X			
Bronchoscopy, baseline BAL and challenge 					X										
Bronchoscopy and post-challenge BAL 												X			
Blood sample for exploratory biomarkers 					X 	X		X				X 			
Blood sample for PK		See footnote 12													
AE review		←-----→													
SAE review		←-----→													
Concomitant medication review		←-----→													

AE: adverse event; BAL: bronchoalveolar lavage; ECG: electrocardiogram; PK: pharmacokinetic; SAE: serious adverse event, C-SSRS: Columbia Suicide Severity Rating Scale.

1. Time points relative to the first dose on Day 1.
2. Admission on Day -1, at a time to allow all Day -1 procedures to be done; discharge on Day 2, at least 4 h after the bronchoscopy.
3. To check for any AEs.
4. Haematology, clinical chemistry (including liver chemistry), cardiac troponins, urinalysis and coagulation profile.
5. Triplicate on Day-1 and pre-dose. Single measurements at time points after dosing.
6. Immediately before BAL sampling/LPS challenge at the 2-h time point.
7. Forced expiratory volume in 1 second (FEV1) and forced vital capacity (FVC). Triplicate measurements at each time point, the highest of which should be recorded in the case report form.
8. Pulse oximetry to be measured during bronchoscopy procedures. Only AEs to be recorded.
9. BAL samples for total protein, neutrophil counts, GSK2798745 and exploratory biomarkers. Baseline BAL sample from a segment in the left lower lobe, followed by segmental challenge of the lungs: LPS in right middle segment; saline control in the lingula segment of the contralateral side. Challenges to be done as close as possible to 2 h post-dose.

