### 2.3. Follow-up/Early Withdrawal

	Follow-up/Early Withdrawal (Day 8 $\pm$ 1 day)
Outpatient visit	X
Full physical examination	X
Weight	X
Laboratory assessments 	X
12-lead ECG 	X
Vital signs 	X
Spirometry 	X
FOBT 	X
AE review	X
SAE review	X
Concomitant medication review	X

AE: adverse event; ECG: electrocardiogram; FOBT: Faecal Occult Blood Test; SAE: serious adverse event.

1. Haematology, clinical chemistry (including liver chemistry), cardiac troponins and urinalysis.
2. Single measurement.
3. Blood pressure, heart rate, temperature. Single measurement.
4. Forced expiratory volume in 1 second (FEV1) and forced vital capacity (FVC). Triplicate measurement, the highest of which should be recorded in the case report form.
5. FOBT cards will be provided upon discharge from the unit and should be returned by the follow-up/early withdrawal visit.

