- *Timing of challenge:* Baseline BAL sampling prior to administration of study drug is not considered feasible due to the burden of bronchoscopy (i.e. two procedures required – one pre and one post dose to instil LPS). A baseline bronchoscopy is planned 2 h after administration of the first dose, with the aim of maximising exposure to GSK2798745 (in healthy volunteers, the median [range] Time to reach maximum plasma concentration (Tmax) of the tablet formulation of GSK2798745 to be used in this study is 1.5 h [1–3 h]). Drug on board at the time of baseline BAL fluid sampling is expected to have little to no effect on baseline BAL total protein concentrations as TRPV4 channels are quiescent until stimulated and blockade of these channels does not affect barrier permeability of ‘healthy’ endothelial cells [internal data]. The effects of LPS to induce endothelial permeability are believed to occur rapidly. Investigation of LPS induced permeability and markers of cell activation and inflammation over time consistently indicates that the initial events leading to increased barrier permeability and inflammation occur within first 2 h post intratracheal (i.t.) LPS exposure; where any earlier measurements are limited. LPS induces intracellular stress fibre formation within 5 min in both human dermal microvascular endothelial cells (HMVEC) endothelial and A549 epithelial cells [Ngamsri, 2010]. Increased levels of TNF $\alpha$  following i.t. LPS instillation are observed within 2 h in man [O’Grady, 2001] and other pro-inflammatory mediators within 4 h in a mouse model of acute lung injury (ALI) [Bosmann, 2012]. Permeability across an endothelial monolayer is observed after 0.5 h and peaks at 2 h post-LPS [Bannerman, 1998]. BAL total protein increases following LPS i.t. challenge in man as early as 2 h and reaches significance at 6 h post-LPS [Matthay, 2012] with significant increases in neutrophil counts also observed as early as 2 h. Looking to a systemic LPS model of sepsis with a higher LPS insult, earlier sampling is possible and high levels of inflammatory mediators are measured within 1 h, which reach plateau by 3 h. Therefore, despite our conservative treatment effect prediction (see Section 5.5), we expect that high plasma and/or alveolar fluid concentrations of GSK2798745 will be required at the time of and/or soon after the challenge, in order to inhibit the effects of LPS. Therefore, LPS will be administered shortly after time of Tmax (1.5-hours) to ensure sufficient drug on board.

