### 9.7.2. Vital Signs

- Vital signs will be measured in a semi-supine position after 5 minutes' rest and will include temperature, systolic and diastolic blood pressure and heart rate
- At each time point before dosing, 3 readings of blood pressure and heart rate will be taken. The first reading should be rejected. The second and third readings should be averaged to give the measurement to be recorded in the CRF. At all other time points, single measurements will be taken.

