12.8.3. Vital Signs

Vital Sign Parameter (Absolute)	Units	Clinical Concern Range	
		Lower	Upper
Systolic Blood Pressure	mmHg	<85	>160
Diastolic Blood Pressure	mmHg	<45	> 90
Heart Rate	bpm	<50	>110

Vital Sign Parameter (Change from Baseline)	Units	Clinical Concern Range			
		Decrease		Increase	
		Lower	Upper	Lower	Upper
Systolic Blood Pressure	mmHg	≥20	≥40	≥20	≥40
Diastolic Blood Pressure	mmHg	≥10	≥20	≥10	≥20
Heart Rate	bpm	≥15	≥30	≥15	≥30

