12.11.7. Safety Tables

Safety: Tables					
No.	Population	IDSL / Example Shell	Title	Programming Notes	Deliverable [Priority]
Adverse Events (AEs)					
3.1.	All Subjects	AE1	Summary of All Adverse Events by System Organ Class and Preferred Term	ICH E3	SAC [1]
3.2.	All Subjects	AE1	Summary All Drug-Related Adverse Events by System Organ Class and Preferred Term/by Overall Frequency	ICH E3	SAC [1]
Serious and Other Significant Adverse Events					
3.3.	All Subjects	AE16	Summary of Serious Adverse Events by System Organ Class and Preferred Term (Number of Participants and Occurrences)	FDAAA, EudraCT	SAC [1]
3.4.	All Subjects	AE1	Summary of Adverse Events Leading to Permanent Discontinuation of Study Treatment or Withdrawal from Study by System Organ Class and Preferred Term	IDSL	SAC [1]
Laboratory: Chemistry					
3.5.	All Subjects	LB1	Summary of Chemistry Changes from Baseline	ICH E3	SAC [1]
Laboratory: Haematology					
3.6.	All Subjects	LB1	Summary of Haematology Changes from Baseline	ICH E3	SAC [1]
Laboratory: Urinalysis					
3.7.	All Subjects	LB1	Summary of Urine Concentration Changes from Baseline	ICH E3	SAC [1]
3.8.	All Subjects	UR3	Summary of Urinalysis Dipstick Results	ICH E3	SAC [1]
Laboratory: Hepatobiliary (Liver)					
3.9.	All Subjects	LIVER1	Summary of Liver Monitoring/Stopping Event Reporting	IDSL	SAC [1]

Safety: Tables					
No.	Population	IDSL / Example Shell	Title	Programming Notes	Deliverable [Priority]
ECG					
3.10.	All Subjects	EG1	Summary of ECG Findings	IDSL	SAC [1]
3.11.	All Subjects	EG2	Summary of Change from Baseline in ECG Values by Visit	IDSL	SAC [1]
3.12.	All Subjects	SAFE_T4	Summary of Number of Participants with Maximum ECG Values Meeting or Exceeding Pre-Specified Ranges of Concern by Category, Treatment and Timepoint.		SAC [1]
Vital Signs					
3.13.	All Subjects	VS1	Summary of Change from Baseline in Vital Signs	ICH E3 Include body temperature, heart rate, blood pressure.	SAC [1]
Columbia Suicide Severity Rating Scale (C-SSRS)					
3.14.	All Subjects	CSSRS1 (SAFE_T1)	Summary of C-SSRS Suicidal Ideation or Behaviour	Include Placebo column.	SAC [1]
Laboratory: Other					
3.15.	All Subjects	SAFE_T2	Summary of Faecal Occult Blood Test (FOBT) Data		SAC [1]
3.16.	All Subjects	LB1	Summary of Cardiac Troponin (cTn) Changes from Baseline		SAC [1]
3.17.	All Subjects	LB1	Summary of Coagulation Profile Changes from Baseline		SAC [1]
Spirometry					
3.18.	All Subjects	SAFE_T3	Summary of Spirometry Data		SAC [1]

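### If a pre-dose blood pressure, heart rate or temperature value is missing, the SAP falls back to a post-dose reading instead of Day -1, and the 1 h change is then zero by construction

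*SAP*

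**What the plan says.** The table of baseline assessments in SAP 5.1, printed just before 5.2, gives Day 1 pre-dose as the display baseline for vital signs and temperature. In the row "Vital signs (blood pressure, heart rate" it marks Screening, Day -1, pre-dose and Day 1 1 h as assessments that may count as baseline. The temperature row has the same marks plus Day 1 2 h. SAP 5.2 then states the fallback: if the designated value is missing, "the study assessment considered as a baseline closest in time to this will replace this as the baseline used in displays". Nothing requires the substitute to precede dosing.

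The number of readings differs by time point. For blood pressure and heart rate the schedule in Protocol 2.2 says: "Triplicate on Day-1 and pre-dose. Single measurements at time points after dosing". Protocol 9.7.2 has three readings at each time point before dosing, with the first discarded: "The second and third readings should be averaged to give the measurement to be recorded in the CRF". The Day 8 visit is again single: "Blood pressure, heart rate, temperature. Single measurement".

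The baseline feeds Table 3.13 (SAP 12.11.7), whose programming note reads "Include body temperature, heart rate, blood pressure". For blood pressure and heart rate it also feeds the thresholds in SAP 12.8.3 headed "Vital Sign Parameter (Change from Baseline", which help decide who appears in Listings 31 and 32.

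**The concern.** A baseline for change-from-baseline safety displays should be an untreated value. Here the substitute is taken after the first dose, although an untreated value from the day before is already on file. On drug timing, Protocol 5.4 says the median Tmax for "the tablet formulation of GSK2798745 to be used in this study is 1.5 h", with a range of 1 to 3 h, so the 1 h reading lies at the start of that range. Protocol 3.3.1 lists an effect on blood pressure through prostaglandin release as a theoretical risk, with blood pressure monitoring as the mitigation. An early effect in an affected active-arm participant would be absorbed into that participant's own baseline.

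The SAP is also not consistent with itself. Section 12.4.1 classes anything after the first dose as post-treatment. Note 3 under the baseline table describes blood pressure and heart rate as triplicate, whereas the 1 h reading it admits is single.

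**Working it through.** **Which assessment the rule selects.** Let p be the hours from the pre-dose reading to the first dose, and d the hours from the Day -1 reading to the first dose.

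- Distance from pre-dose to 1 h: p + 1.
- Distance from pre-dose to Day -1: d − p.
- The 1 h reading is chosen when p + 1 < d − p, that is, p < (d − 1)/2.

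Dosing is in the morning of Day 1 (Protocol 7.1); clock times are not given. Assume dosing between 07:00 and 10:00 and Day -1 readings between 14:00 and 22:00, so d runs from 9 h (22:00 to 07:00) to 20 h (14:00 to 10:00). The limit for p is then (9 − 1)/2 = 4.0 h to (20 − 1)/2 = 9.5 h. A pre-dose reading 0.5 to 2 h before dosing is 1.5 to 3 h from the 1 h reading and 7 to 19.5 h from Day -1, so 1 h is chosen throughout. For temperature, 1 h is always nearer than 2 h. If 1 h is missing too, the 2 h reading is 2.5 to 4 h away and still beats Day -1.

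**What happens to the changes.** Let δ = (substitute value) − (true pre-dose value). Reported change = true change − δ. With the 1 h reading as substitute, the true 1 h change is δ, so the reported 1 h change is δ − δ = 0. Blood pressure and heart rate have six post-dose assessments (1, 6, 12, 14 and 30 h, Day 8): one is fixed at zero and five are shifted.

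**Illustration (assumed systolic values).** Pre-dose missing, Day -1 120, 1 h 145, 14 h 130 mmHg.

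| | Baseline | Change at 1 h | Change at 14 h |
|---|---|---|---|
| SAP rule (1 h) | 145 | 0 | −15 |
| Day -1 fallback | 120 | +25 | +10 |

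The +25 meets the 20 mmHg increase threshold in 12.8.3. Under the SAP rule it is not flagged, and 145 does not exceed the absolute limit of 160 mmHg.

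**Flag thresholds.** For systolic δ = −5, −10 or −20 mmHg, the 20 mmHg decrease flag needs a true fall of 20 − δ = 25, 30 or 40 mmHg, and the increase flag needs a true rise of 20 + δ = 15, 10 or 0 mmHg. Signs reverse for δ > 0. This algebra holds for any substitute, Day -1 included.

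**How many participants.** The missing rate q is an assumption. With n per arm, the expected number affected is nq and the chance of at least one is 1 − (1 − q)^n, taking participants as independent.

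| q | n = 30 | n = 20 | n = 10 |
|---|---|---|---|
| 0.5% | 0.15; 14% | 0.10; 10% | 0.05; 5% |
| 1% | 0.30; 26% | 0.20; 18% | 0.10; 10% |
| 5% | 1.50; 79% | 1.00; 64% | 0.50; 40% |

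The smaller n correspond to stopping at an interim analysis. The 5% row is an outer bound, not an expectation: participants are resident from Day -1, and blood pressure and heart rate are read three times before dosing. In a 30-participant arm, one affected participant with δ = −10 mmHg moves the mean later change by 10/30 = 0.33 mmHg.

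**The case against.** The best defence is that the marks are deliberate. Every vital sign scheduled after dosing but before the LPS challenge is marked, and nothing after it. A same-morning, pre-challenge value is a defensible reference in an LPS study in which pyrexia is a known risk. But the SAP does not state this reason, its study phases are defined by the first dose alone, and Day -1 also precedes LPS. Nothing on that ground is lost by using Day -1.

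Second, a Day -1 value is not the true pre-dose value either. It comes from the previous day at an unstated hour, and nothing in the documents shows it lies closer. This stands. The shifted later changes and moved flag thresholds are not specific to the 1 h reading. What is specific is the forced zero, the possible drug effect in the baseline and, for blood pressure and heart rate, the single reading.

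Third, a reader might take the ECG and spirometry rows, which list no post-dose time, as proof that the SAP intended pre-dose substitutes only. They prove nothing of the kind: neither is scheduled at 1 h or 2 h, so there was no mark to leave out.

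Finally, whether Table 3.13 would actually print the zero depends on a sponsor standard shell that is not in the documents, and Protocol 3.3.1 reports no blood pressure effect of the drug to date. Both points limit the consequence; neither changes which value the rule selects.

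**Conclusion.** The point holds as a minor defect in the fallback rule. Read as written, SAP 5.2 replaces a missing pre-dose value with a post-dose reading although an untreated Day -1 value exists. The only assumption behind that selection is that pre-dose readings are taken within a few hours of the morning dose. For an affected participant in either arm the 1 h change carries no information; in the active arm the baseline may also contain drug effect.

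A reader might infer that the rule could hide a vital-sign signal or distort the comparison between arms. The documents do not support that. The rule applies only when a pre-dose value is missing, which should be rare, and the effect on arm means is negligible. The absolute-value flags still apply at 1 h. Temperature has no threshold in 12.8.3, so for temperature only Table 3.13 is touched. Safety data are not formally tested (Protocol 10.3.2), no protocol stopping criterion sets a threshold on change in vital signs, and the primary analysis does not use these values. This is an optional correction of low priority.

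**What to change.** In the SAP baseline table, delete the Day 1 1 h mark for blood pressure and heart rate, and the Day 1 1 h and 2 h marks for temperature. The wording of 5.2 can stay: a missing pre-dose value then falls back to Day -1 and, failing that, to Screening. The substitute is then off-drug, precedes LPS, comes from triplicate readings for blood pressure and heart rate, and leaves the 1 h change free to vary.

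The cost is three marks in one table. No new data, visit, procedure or protocol amendment is needed, because the Day -1 values are already collected.

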5.3. Examination of Covariates, Other Strata and Subgroups**5.3.1. Covariates and Other Strata**

The list of covariates and other strata may be used in descriptive summaries and statistical analyses, some of which may also be used for subgroup analyses. Additional covariates and other strata of clinical interest may also be considered.

Category	Details
Covariates	Baseline (2h) total protein, 26h total protein (saline lobe)

NOTES:

- The covariates listed are those that may be used in analyses.

The default statistical model for BAL markers is to fit an analysis of covariance (ANCOVA) model with baseline (2h BAL) response and treatment group as covariates and 26h BAL response as the response variable. Additional covariates with the use of clinical expertise and statistical tools (raw plots and model selection criteria) may be considered such as age and gender.

5.3.2. Examination of Subgroups

There are no planned subgroup analyses.

5.4. Multiple Comparisons and Multiplicity

Due to the extensive use of a Bayesian framework and the early phase/exploratory nature of this study there will be no explicit multiplicity adjustments. Moreover, the decision framework for study success/fail is predetermined.

5.5. Other Considerations for Data Analyses and Data Handling Conventions

Other considerations for data analyses and data handling conventions are outlined in the appendices:

Section	Component
12.3	Appendix 3: Assessment Windows
12.4	Appendix 4: Study Phases and Treatment Emergent Adverse Events
12.5	Appendix 5: Data Display Standards & Handling Conventions
12.6	Appendix 6: Derived and Transformed Data
12.7	Appendix 7: Reporting Standards for Missing Data
12.8	Appendix 8: Values of Potential Clinical Importance

6. STUDY POPULATION ANALYSES

6.1. Overview of Planned Study Population Analyses

The study population analyses will be based on the All Subjects population, unless otherwise specified.

Study population analyses including analyses of participants' disposition, protocol deviations, demographic and baseline characteristics, prior and concomitant medications, and exposure and treatment compliance will be based on GSK Core Data Standards. Details of the planned displays are presented in [Appendix 11: List of Data Displays](#).

7. PHARMACODYNAMIC AND BIOMARKER ANALYSES

7.1. Primary Pharmacodynamic and Biomarker Analyses

7.1.1. Endpoint / Variables

The primary endpoint is defined as BAL total protein (in the lobe in which LPS was administered) at 26h post first dose (24 hours after segmental LPS challenge). A Bayesian framework will be used (with non-informative priors on all model parameters) to estimate the posterior probability of any percentage reduction in mean 26 h BAL protein level (GSK2798745 relative to placebo). It is anticipated that BAL total protein will be log_e transformed to improve normality before model fitting. Following back-transformation treatment comparisons will be expressed as percentage changes. Details of data transformations are described in [Appendix 6: Derived and Transformed Data](#).

7.1.2. Summary Measure

Following back-transformation, treatment comparison will be expressed as an adjusted median posterior percentage reduction in 26h total protein level for GSK2798745 compared to placebo, along with corresponding 95% credible interval.

7.1.3. Population of Interest

The primary analyses will be based on the Evaluable population.

7.1.4. Strategy for Intercurrent (Post-Randomization) Events

Since this is a proof of mechanism study, the estimand of interest in the primary analysis is the treatment effect (GSK2798745 c.f. placebo) for participants in the Evaluable population i.e. all randomised participants who received the two correct doses of study treatment, received LPS and saline segmental challenge (in contralateral lobes) and for which results for both baseline (2h) and 26h (LPS lobe) BAL samples are evaluable and did not have any major deviations affecting the primary endpoint. Given that the primary analyses are based on the Evaluable population in healthy participants, any intercurrent events such as treatment discontinuation will result in exclusion of the data from the analysis and no missing data imputation will occur.

